9.4 Glucodynamic Assessment

9.4.1 Glucodynamic Parameter Estimation

The “GD” population for the statistical inference is defined in Section 8.

Also, for Days 1 and 3 and Day 2, separately, patients who did not complete the entire test meal or had significant changes in nutrient consumption (greater than 10%) of the test meal or dose changes during the breakfast test meal will be excluded from all the GD analyses.

Data will be analyzed for the patients during each MMTT. The change from baseline values (the average of -30, -15, and 0 minutes represented as the 0-hour time point) for each patient will be calculated. Incremental change from baseline glucose AUC values will be calculated during a 5-hour meal test. Partial AUCs may be calculated as deemed appropriate. Parameters will be calculated and provided to Covance by Lilly. Parameters will include:

- BGAUC(0-30 min)
- BGAUC(0-1 h)
- BGAUC(0-2 h)
- BGAUC(0-3 h)
- BGAUC(0-4 h)
- BGAUC(0-5 h)
- BGAUC(2.5-5 h)
- Maximum change from baseline (BG_{max})
- Maximum change from baseline up to 1 h (BG_{1h})
- Maximum change from baseline up to 2 h (BG_{2h})

9.4.2 Glucodynamic Statistical Inference

Summary statistics (including number of patients, mean, standard deviation or standard error, minimum, and maximum) will be presented by treatment and by bolus dose administration mode (all 4 combinations of treatment) for Days 1 and 3 (and combined) and Day 2, separately. The same statistical model and comparisons used to analyze the PK parameters will be used to analyze the GD parameters on the original scale (not log-transformed) using Fieller's theorem (Chow and Liu 2009³). A macro provided by Lilly will be used to complete the Fieller's theorem analysis.

The analysis will be repeated for the completers population.

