3. INTRODUCTION

This SAP has been developed after review of the Clinical Study Protocol (final version dated 19 November 2016 and amendment (a), dated 6 February 2017).

This SAP describes the planned analysis of the safety, tolerability, pharmacokinetic (PK) and glucodynamic (GD) data from this study. A detailed description of the planned TFLs to be presented in the clinical study report (CSR) is provided in the accompanying TFL shell document.

The intent of this document is to provide guidance for the statistical and PK analyses of data. In general, the analyses are based on information from the protocol, unless they have been modified by agreement between Eli Lilly and Company and CCI. A limited amount of information concerning this study (e.g., objectives, study design) is given to help the reader's interpretation. This SAP must be signed off prior to first patient administration for this study. When the SAP and TFL shells are agreed upon and finalized, they will serve as the template for this study's CSR.

This SAP supersedes the statistical considerations identified in the protocol; where considerations are substantially different, they will be so identified. If additional analyses are required to supplement the planned analyses described in this SAP, they may be performed and will be identified in the CSR. Any substantial deviations from this SAP will be agreed upon between Eli Lilly and Company and CCI and identified in the CSR. Any minor deviations from the TFLs may not be documented in the CSR.

This SAP is written with consideration of the recommendations outlined in the International Council on Harmonization (ICH) E9 Guideline entitled Guidance for Industry: Statistical Principles for Clinical Trials¹ and the ICH E3 Guideline entitled Guidance for Industry: Structure and Content of Clinical Study Reports².

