4.2 Secondary Objectives

- To evaluate the sustainability of any difference in insulin lispro PK of LY900014 and Humalog over 3 days when administered as different test bolus doses with an insulin pump to patients with T1DM during a breakfast meal test.
- To evaluate the difference in GD response when LY900014 and Humalog are administered as different test bolus doses with an insulin pump to patients with T1DM during a breakfast meal test.

- To compare the durability of GD response over 3 days when LY900014 and Humalog are administered as different test bolus doses with an insulin pump to patients with T1DM during a breakfast meal test.

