9. STATISTICAL METHODOLOGY

9.1 General

Data listings will be provided for all data that is databased. Summary statistics and statistical analysis will only be presented for data where detailed in this SAP. For continuous data, summary statistics will include the arithmetic mean, arithmetic standard deviation, median, min, max and N; for log-normal data (e.g. the PK parameters: AUCs and C_{max}) the geometric mean and geometric coefficient of variation (CV%) will also be presented. For categorical data, frequency count and percentages will be presented. Data listings will be provided for all patients up to the point of withdrawal, with any patients excluded from the relevant population

highlighted. Summary statistics and statistical analyses will generally only be performed for patients included in the relevant analysis population. For the calculation of summary statistics and statistical analysis, unrounded data will be used.

Mean change from baseline is the mean of all individual patients' change from baseline values. Each individual change from baseline will be calculated by subtracting the individual patient's baseline value from the value at the timepoint. The individual patient's change from baseline values will be used to calculate the mean change from baseline using a **CCI** [REDACTED].

Unless otherwise specified, testing for significance is all done at an α -level of 0.1 with 2-sided confidence intervals (CIs). Statistical significance will be claimed if the p-value of a test is less than 0.1.

Data analysis will be performed using **CC** [REDACTED].

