9.3.2 Pharmacokinetic Statistical Inference

The “PK” population for the statistical inference is defined in Section 8.

Log-transformed insulin lispro T_{max}, early 50% T_{max}, late 50% T_{max}, C_{max}, t_{1/2}, and AUC estimates will be evaluated to estimate geometric means, ratios of geometric means of insulin lispro within LY900014 to Humalog by day and bolus administration mode, and the corresponding 90% CIs of the ratios.

The statistical model for the Day 1 and Day 3 breakfast meal tests will include treatment (4 combinations of treatment and bolus administration mode: LY900014 dual-wave, Humalog dual-wave, LY900014 single-wave, or Humalog single-wave), period, day (Day 1 or Day 3), and treatment-by-day interaction as fixed effects and patient as a random effect.

Example SAS code:

```
proc mixed data=pk;
  class patient treatment period day ;
  model logpk = treatment period day treatment*day / ddfm=kr;
  lsmeans trt*day;
  random patient / grp= treatment;
  repeated / grp= treatment;
run;
```

A separate analysis model will be used for the Day 2 breakfast meal test, including treatment (4 combinations of treatment and bolus administration mode: LY900014 rapid, LY900014 standard, Humalog rapid, or Humalog standard, all given as a single-wave bolus) and period as fixed effects and patient as a random effect.

Example SAS code:

```
proc mixed data=pk;
  class patient treatment period;
  model logpk = treatment period / ddfm=kr;
  random patient / grp= treatment;
  repeated / grp= treatment;
run;
```

For the primary inference, insulin lispro administered from LY900014 will be concluded to have a significantly decreased early 50% T_{max} relative to Humalog if the upper confidence bound of the 2-sided 90% CI of the ratio of geometric means of the early 50% T_{max} is <1 .

If possible, the above models will also be used to calculate the intra-patient and inter-patient variability of LY900014, however if convergence issues occur, then the model will be appropriately updated to account for these issues.

As a sensitivity analysis, early 50% T_{max} will be analyzed by day using the Wilcoxon signed-rank test. The difference in median early 50% T_{max} between LY900014 and Humalog and the 90% CIs for the difference will be presented.

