9.5.10 Exploratory Continuous Glucose Monitoring Analyses

The CGM outcome variables will be derived based on the raw data collected from the individualized standardized lunch meals on Days 1, 2, and 3 and from the individualized standardized dinner meals on Days 1 and 2.

The following incremental glucose AUCs will be calculated:

- AUC(0-1 h)
- AUC(0-2 h)
- AUC(0-5 h)

- AUC(2.5-5 h)

The incremental glucose AUCs will be calculated using the linear trapezoidal method (with negative areas included in the calculation of the trapezoidal areas). For the calculation of the incremental glucose AUC parameters, baseline is defined as the average of all CGM values recorded in the 19 minutes prior to each meal.

For the CGM data, time in range parameters will be derived from the raw data collected through the 3 days of CGM device use by patient, treatment, bolus dose administration method and meal. The following ranges will be calculated:

- Normal range (>70 mg/dL and ≤ 180 mg/dL) for each day, normalized to 5 hours (duration and % of 5 hours)
- Strict normal range (>70 mg/dL and ≤ 140 mg/dL) for each day, normalized to 5 hours (duration and % of 5 hours)
- Hyperglycemia (>180 mg/dL) during the treatment period, normalized to 5 hours (duration and also as % of 5 hours)
- Hypoglycemia (≤ 70 mg/dL) during the treatment period, normalized to 5 hours (duration and % of 5 hours)
- Severe hypoglycemia (≤ 55 mg/dL) during the treatment period, normalized to 5 hours (duration and % of 5 hours)

For the calculation of the incremental glucose AUCs and range parameters, the following rules will be used to define a valid CGM session prior to parameter calculation:

- Minimum number of measures for each parameter must be greater than 70% of the total measures obtained. For example, for iAUC(0-2 h), there will be 24 measurements during this period so a patient must have at least 17 valid measurements to be able to calculate the parameter. Similarly, for the time in range parameters calculated over 5 hours, there will be 60 measurements so must be at least 42 valid measurements to be able to calculate these parameters

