- The maximum allowable continuous missing interval will be 10 minutes for incremental glucose AUC(0-1 h), 20 minutes for incremental glucose AUC(0-2 h) and incremental glucose AUC(2.5-5 h), and 25 minutes for incremental glucose AUC(0-5 h), Low blood glucose index (LBGI), high blood glucose index (HBGI), combined blood glucose risk index (BGRI, sum of the LBGI and HBGI), and the time in range parameters

The incremental glucose AUCs and time in range parameters will also be analyzed statistically with separate analyses based on the parameters at lunch times on Days 1, 2 and 3 only, and based on the parameters at Dinner times on Days 1 and 2 only. The model will include treatment (combination of treatment and bolus administration mode), period and day within period and treatment- by-day within period as fixed effects, and patient as a random effect. The model will be used to estimate least squares means, differences of least squares means of insulin lispro within LY900014 to Humalog by bolus administration mode, and the corresponding 90% CIs of the ratios.

In addition to the above parameters, within-day and between-day CGM variability parameters will be calculated. The within-day parameters (derived by day and meal) will include the standard deviation, CV% and Mean amplitude of glycemic excursions (MAGE). The between-day parameters will be based on the lunch data on Day 1-3 and dinner data on Days 1-2 separately, and will include the standard deviation, CV% and mean of daily differences (MODD).

The LBGI, HBGI and BGRI will also be derived. The LBGI has been developed to quantitate both frequency and severity of hypoglycemia. The LBGI has been validated as a predictor of severe hypoglycemia, which is a serious adverse event and could result in coma or death if unrecognized and untreated. The HBGI quantifies both frequency and severity of hyperglycemia and has been related to HbA1c and risk for hyperglycemia (Kovatchev et al. 2005). Additionally, both the LBGI and HBGI have a high sensitivity to changes in glycemic profiles and control (Kovatchev et al. 2005). LBGI is a non-negative number that increases as the number of low readings increases. HBGI is a non-negative number that increases as the number of high readings increases.

The LBGI, HBGI, and BGRI will be derived in the following steps:

Step 1: For each blood glucose (BG [mg/dL]) at the i^{th} time point, compute the following:

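### SAP 9.4.2 states only ratio comparisons with Fieller intervals for breakfast glucose changes; LS mean differences should be added, because a ratio interval can be unbounded when the Humalog mean is near zero

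*SAP*

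**What the plan says.** SAP 9.4.2, in line with Protocol 10.3.3.2, says that the PK model and comparisons "will be used to analyze the GD parameters on the original scale (not log-transformed"), using Fieller's theorem. A sponsor macro carries out the Fieller step.

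SAP 9.4.2 does not itself use the word ratio. That reading follows from two facts. SAP 9.3.2 defines the model-based PK comparisons as "ratios of geometric means of insulin lispro within LY900014 to Humalog by day and bolus administration mode", with 90% CIs, and Fieller's theorem is an interval method for a ratio of means. The only difference named in the PK section is the median difference in the Wilcoxon sensitivity analysis of early 50% Tmax. For breakfast glucose the text adds descriptive summaries by treatment and mode, but no difference of LS means.

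The parameters are changes from baseline. SAP 9.4.1 says: "Incremental change from baseline glucose AUC values will be calculated during a 5-hour meal test". Its list includes BGAUC(0-5 h), several partial areas including BGAUC(2.5-5 h), and three maximum changes. It does not say how area below baseline is treated. SAP 9.5.10 does say so for the lunch and dinner CGM areas: "with negative areas included in the calculation of the trapezoidal areas". For those parameters it also names the contrast, but attaches the wrong interval to it: "differences of least squares means of insulin lispro within LY900014 to Humalog by bolus administration mode, and the corresponding 90% CIs of the ratios".

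On testing, SAP 9.1 says: "Statistical significance will be claimed if the p-value of a test is less than 0.1". On outputs, SAP 3 says that the detailed description of the tables "is provided in the accompanying TFL shell document". Neither that document nor the macro was available for this review.

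**The concern.** A ratio of means is informative when the denominator is well away from zero. PK areas and times are positive, so the ratio is natural there. A change from baseline has no such floor. If areas are signed, the Humalog mean can be small or negative, most plausibly late in the meal test. On Days 1 and 3 glucose is brought to 126 (±20) mg/dL before the meal (Protocol 5.1.1.2), and the dual-wave mode spreads half the bolus over 3 hours, so delivery runs into the 2.5-5 h window.

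Two things can then go wrong in the report. The 90% Fieller set may have no finite limits, so a comparison has no usable interval for its size. And if the Humalog mean is negative, a ratio below 1 means that glucose was higher on LY900014, the opposite of the usual reading. Neither document gives a rule for either case. The glucose ΔAUC is the only endpoint of both secondary GD objectives, so a finite interval in glucose units for the treatment effect is worth having. The planned summary means would show the sign, but give no CI for the effect.

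**Working it through.** **The plan's own figure.** The only power statement concerns early 50% Tmax, and it reproduces. With ln 0.75 = -0.2877, within-patient SD = √ln(1 + 0.359²) = 0.3482 and SE = 0.3482 × √(2/20) = 0.110, power at two-sided 0.1 is 80.9% (noncentral t, 19 df), against about 80% stated. It does not bear on this point. The documents give no mean or SD for any glucose parameter, so the rest is shown over assumed ranges.

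**Inputs.** From the SAP: 20 completers (24 randomized) and 90% two-sided intervals. Assumed: the true Humalog mean/SD, the within-patient correlation, and paired normal data as an approximation to the mixed model.

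**When the set is unbounded.** Let m_T and m_R be the LY900014 and Humalog means, v_T and v_R their variances, and c their covariance. The Fieller set holds every θ with

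(m_T − θ·m_R)² ≤ t²·(v_T − 2θc + θ²v_R).

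The coefficient of θ² is m_R² − t²v_R. The set is bounded only if this is positive, that is, if |m_R| > t × SE(m_R).

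- n = 20: 1.729/√20 = 0.387 SD
- n = 24: 1.714/√24 = 0.350 SD

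**Chance per comparison** (noncentral t, noncentrality √n × mean/SD):

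| Assumed true Humalog mean/SD | Unbounded, n = 20 | Unbounded, n = 24 | Observed Humalog mean ≤ 0, n = 20 |
|---|---|---|---|
| 0.5 | 30% | 23% | 1.3% |
| 0.75 | 6% | 3% | below 0.1% |
| 1.0 | 0.4% | 0.1% | – |
| 1.5 or more | about 0 | about 0 | – |

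At a mean/SD of 0.2 the chances with 20 completers are 78% (unbounded) and 19% (observed mean ≤ 0).

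**Illustration.** Take n = 20, assumed SD 150 mg·h/dL, correlation 0.5 and an observed difference of -40. The 90% CI of the difference is -40 ± 1.729 × 150 × √(2 × 0.5/20) = -40 ± 58, or -98 to 18, whatever the Humalog mean.

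| Humalog mean | 90% Fieller set for the ratio |
|---|---|
| 200 | 0.55 to 1.11 |
| 100 | 0.03 to 1.27 |
| 60 | -6.1 to 2.05 |
| 40 | whole real line |
| -40 | everything outside -2.43 to 0.71 |
| -100 | 0.86 to 2.86 (above 1 now means lower glucose on LY900014) |

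For assumed SDs of 75 to 200 mg·h/dL, the set is unbounded when the Humalog BGAUC(2.5-5 h) mean is within 29 to 77 mg·h/dL of zero. Divided by 2.5 h, that is a mean glucose change of about 12 to 31 mg/dL.

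**Effect on the test.** Put θ = 1 in the inequality. It becomes (m_T − m_R)² ≤ t²·Var(m_T − m_R), which is the condition for the difference CI to include 0. So the set excludes 1 exactly when the difference CI excludes 0, given the same covariance and degrees of freedom. In simulation (40,000 trials per case, 26 cases) the two agreed every time, unbounded sets included. In the illustration every Fieller set contains 1, as the difference CI contains 0.

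**The case against.** The strongest reply is that the harm needs three conditions that the documents do not establish: the ratio is the only contrast produced, areas are signed, and the Humalog mean is near zero. The tables may already contain differences. The specified model yields LS means, and the example code for Days 1 and 3 requests them by treatment and day. This stands. The point is therefore limited to the text of SAP 9.4.2 and is conditional on the other two.

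A reader might infer that ratios contradict the objective, which is worded "To evaluate the difference in GD response when LY900014 and Humalog are administered as different test bolus doses". They do not. The primary PK objective uses the same word and is analysed by ratios, so in these documents it does not mean an arithmetic difference.

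A reader might also dwell on how often a significant result would lack a finite interval. With a true difference of -0.5 SD and correlation 0.5, 69% of simulated trials were significant. At a Humalog mean/SD of 0.5, 21% of those had an unbounded set. But that case sets the true LY900014 mean to 0.5 − 0.5 = 0, a complete abolition of the excursion, and it conditions on significance. Over all trials the share is 0.69 × 0.21, or about 14.5%. At 0.75 the conditional figure is 2.4%, and at 1.0 it is 0.1%. It is not a fair headline.

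The possible 30% increase in the meal dose does not show that late glucose will fall below baseline. It is conditional, and Protocol 5.5 cites extra requirements of 17% to 124%. Finally, Fieller ratios are prespecified in the protocol, and nothing here justifies demoting them.

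**Conclusion.** The point holds as a modest reporting gap. The text of SAP 9.4.2 names no LS mean difference for breakfast change-from-baseline glucose, and the ratio that it implies can lack a finite interval or reverse direction if areas are signed and the Humalog mean is close to zero. BGAUC(2.5-5 h) is the most plausible case; that is a judgment, and no objective names this parameter. BGAUC(0-5 h) is only possibly exposed. Early windows and maximum changes are not expected to be.

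The size depends wholly on the unknown mean/SD: material at 0.5 or below, small at 0.75, negligible from 1.0. The figures use a paired approximation. The specified model has treatment-specific variances and Kenward-Roger degrees of freedom, so exact values will differ somewhat.

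A reader might conclude that a secondary test is lost or biased. It is not: the conclusion at the 0.1 level is the same with either interval, and the primary PK inference is untouched. The slip in SAP 9.5.10 is separate and exploratory. It needs correcting under any assumption, but adds no weight to the main point.

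**What to change.** In SAP 9.4.2, add LS mean differences (LY900014 minus Humalog, by day and bolus mode) with 90% CIs, from the mixed model already specified, for all change-from-baseline GD parameters. Keep the prespecified Fieller ratios alongside for every comparison, and label any unbounded ratio set and any non-positive Humalog mean. Do not drop ratios according to how they turn out. Identify the addition as SAP 3 requires. The difference has a finite interval under either sign rule, so this change does not wait on a clarification of SAP 9.4.1.

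In SAP 9.5.10, make the interval match the contrast: 90% CIs of the differences rather than of the ratios.

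The cost is wording in two sections, one extra set of estimates per parameter, and possible edits to the TFL shells, which SAP 3 makes the template for the study report. No new model, data or patients are needed.

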9.5 Safety and Tolerability Assessments

9.5.1 Adverse events

Where changes in severity are recorded in the Case Report Form (CRF), each separate severity of the adverse event (AE) will be reported in the listings, only the most severe will be used in the summary tables. A pre-existing condition is defined as an AE that starts before the patient has provided written informed consent and is ongoing at consent. A non-treatment emergent AE is defined as an AE which starts after informed consent but prior to dosing. A treatment-emergent AE is defined as an AE which occurs postdose or which is present prior to the first dose and becomes more severe postdose. Any AE that occurs during the outpatient period will be associated with open-label Humalog (and not treatment).

All AEs will be listed. Treatment-emergent AEs will be summarized by treatment, bolus administration mode, meal, severity and relationship to the study drug. The frequency (the number of adverse events, the number of patients experiencing an adverse event and the percentage of patients experiencing an adverse event) of treatment-emergent adverse events will be summarized by treatment, bolus administration mode, meal, Medical Dictionary for Regulatory Activities (MedDRA) version 19.1 system organ class and preferred term. The summary and frequency adverse event tables will be presented for all causalities and those considered related to the study drug. Any serious adverse events will be tabulated.

